13.4 Blinding of Study

The blinded TMS coils will arrive from Neuronetics and will be identical in appearance and labeled generically (e.g., Coil X, Coil Y). The device will recognize one coil as active and the other coil as sham. Once a subject has been randomized, the device will "link" the subject's treatment with the corresponding coil. The device will remain inactive if the "incorrect" coil is used for a subject, adding an additional safeguard for each subject and the integrity of the study and allowing the study treaters to remain blinded to the nature of the subject's treatment assignment.

Subjects will be randomly assigned to a coil and will receive all treatments during Phase I of the trial using this coil. Neither the subject nor the study staff (including those administering TMS treatments and those administering mood, cognitive, safety, and imaging assessments) will know whether the subject is

Page 35 of 61

receiving active or sham treatment. Subjects and Parents (if subject < 18 years old or does not meet the local or state legal age requirement) will complete a Pre/Post-Treatment Expectations and Experience Questionnaire (PRE-TEEQ-A/PRE-TEEQ-P and POST-TEEQ-A/POST-TEEQ-P) that queries their initial expectations of trial outcome and final impression of the trial.

In Phase II and III, all treatments will be provided with the known-active coil.

To minimize any source of bias, unblinding of the study will not be done until all subjects have completed all study phases. However, unblinding will occur if the Data and Safety Monitoring Board, consistent with their assigned charter and associated stopping rules, determines that it necessary to do so.

As an additional measure to ensure the integrity of the blinded coil assignment, the study coils at each location may be retrieved by Neuronetics study personnel and new study coils re-assigned.

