## Section 7. Efficacy Analyses

## A. Efficacy Objectives:

The specific efficacy outcome variables, the time points of observation, and the data sets for analysis of these variables are summarized in Table 8. For each of the measures, the scoring conventions are shown in the Attachment at the end of this statistical plan. Statistical differences will be assessed between groups in phase I. Data analysis in phase II and III will be descriptive.

**NOTE**: The timing of assessment of the primary outcome measure is blinded to the investigator's and study team's view and is not specified in the protocol. This information is contained in the statistical plan summary document here, and should not be provided to any study personnel under any circumstances.

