## J. Auditory Threshold Testing:

Air conduction auditory threshold is obtained at baseline, and repeated up to 3 additional time points in the study depending upon the subject's participation in the various study phases (see Schedule of Events above). Air conduction threshold results are reported as means of right and left dB readings for each of the 8 specified test frequencies across the baseline and end of study phase time points, and the change in dB readings from baseline at the end of study phase time points, using a standard audiogram format and summarizing by study group.

For each of the 8 specified test frequencies both the observed outcome and the change from baseline to end of study phase will be summarized (using the standard audiogram format as noted above). The treatment groups will be compared with respect to the baseline outcome and the change from baseline to end of study phase. The null hypothesis of the equality of the treatment group means will be tested using a t-test. Within each treatment group the statistical significance of the mean change from baseline to end of study phase will be assessed using a paired t-test. For each treatment group the data will be summarized showing the sample size, mean, median, standard deviation, minimum, and maximum.

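### SAP 8.J does not limit its hearing t-tests to Phase I; read naturally, it also tests groups at the end of Phases II and III, where the contrast is not randomised active versus sham

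*SAP*

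**What the plan says.** SAP Section 8.J takes air-conduction thresholds at baseline, "repeated up to 3 additional time points in the study depending upon the subject's participation in the various study phases". Among the results to be reported it lists "the change in dB readings from baseline at the end of study phase time points".

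The testing plan follows, for each of 8 frequencies. The groups are compared on the baseline value and on the change: "The treatment groups will be compared with respect to the baseline outcome and the change from baseline to end of study phase". The method is an unadjusted test: "The null hypothesis of the equality of the treatment group means will be tested using a t-test". Within each group, the mean change "will be assessed using a paired t-test". 8.J names no phase for these tests, no covariate and no alpha level.

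Three other places bear on this:

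- SAP Section 7.A, under Efficacy Analyses: "Statistical differences will be assessed between groups in phase I. Data analysis in phase II and III will be descriptive". Section 8 (Safety Analyses) has no such sentence.
- Protocol Section 13.4: "In Phase II and III, all treatments will be provided with the known-active coil".
- SAP Sections 3.A.2 and 3.A.3: Phase II is offered to subjects without protocol-defined benefit in Phase I, and Phase III follows those who had it in Phase I or II.

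**The concern.** Randomisation supports an active-versus-sham comparison at the end of Phase I. After that, entry to each phase depends on a post-randomisation outcome, and any further stimulation is active. A t-test between the original arms at those later points mixes selection with unequal cumulative exposure. A paired test in the group first assigned to sham, taken from the Phase I baseline to the end of Phase II, measures change across a period that contains an active course.

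Protocol Section 8.4 names a change in auditory threshold as a potential risk, and acute and long-term safety is a secondary objective (SAP Section 1.C). P-values that look like treatment comparisons but are not would enter that part of the safety evidence. A smaller matter is that the valid Phase I test leaves unused a baseline measurement that is already collected.

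**Working it through.** The documents give no power, alpha or expected shift for hearing, so there is no planned hearing figure to reproduce. The checks below use stated counts, with assumptions marked.

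**1. Exposure at each audiometry.** SAP Section 3.A.2 gives maxima by the end of Phase II of 66 active sessions (randomised to active) and 36 (randomised to sham). These reproduce, taper included: 30 + 36 = 66 and 0 + 36 = 36. The schedules (Protocol Appendices A and B; SAP Section 3.B) place audiometry at week 6, before taper, so the figures that apply to hearing are:

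- Phase I week 6: up to 30 versus 0 active sessions.
- Phase II week 6: up to 30 + 30 = 60 versus 0 + 30 = 30.
- Phase III month 6: mixed histories. Benefit on active in Phase I, sham then active, and active then active are all possible. So is benefit on sham in Phase I, with no active TMS unless retreated.

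**2. What the Phase II contrast estimates.** Let one active course shift the threshold by d dB.

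- Phase I: the contrast is d.
- Phase II: the contrast is d if courses add up (2d − d), and 0 if the effect levels off after one course (d − d).

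The Phase II contrast therefore measures the second course's increment, in a selected set.

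**3. Size of the sets.** The Protocol Study Summary expects 42 subjects in Phase II and 37 in Phase III. The detectable standardised difference at 80% power, two-sided 5%, is (1.96 + 0.84) × √(2/n per group):

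- Phase I, n = 50: 0.56 SD.
- Phase II, n = 21 (even split assumed): 0.86 SD.
- Phase III, n = 18.5 (even split assumed): 0.92 SD.

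**4. Selection.** A simulation assumed that 42% do not benefit, that the efficacy effect is 0.5 to 0.6 SD (the range in SAP Section 2.A), and that there is no true hearing effect. The Phase II set is then about 36% to 38% randomised to active. The active-minus-sham difference in hearing change there is:

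- 0 if hearing change is unrelated to depression outcome;
- about −0.07 to −0.09 SD at a correlation of 0.2;
- about −0.13 to −0.16 SD at a correlation of 0.4.

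The correlations are assumptions; the documents give none.

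**5. Number of tests**, with one value per frequency and an assumed 5% level:

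- All three phases: 8 × [1 baseline + 3 × (1 between-group + 2 paired)] = 80; 80 × 0.05 = 4 expected by chance if every null holds.
- Phase I only: 8 × (1 + 1 + 2) = 32; 32 × 0.05 = 1.6.

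Correlation between frequencies does not alter these expectations. For the between-group change tests alone, the chance of at least one false positive under independence is 1 − 0.95^8 = 34% (Phase I only) or 1 − 0.95^24 = 71% (three phases). Positive correlation would lower both.

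**6. Baseline adjustment in Phase I.** With equal variances at baseline and week 6 and correlation r, the change score has variance 2(1 − r)σ² and ANCOVA has (1 − r²)σ². The ratio is (1 + r)/2:

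- r = 0.5: 0.75, or 25% less variance.
- r = 0.7: 0.85, or 15% less.
- r = 0.9: 0.95, or 5% less.

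The documents give no r.

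**The case against.** The strongest reply is that 8.J never says the tests are run after every phase. The plural time points occur in the reporting sentence, while the testing sentences speak of the end of study phase in the singular. Section 7.A could be taken as the general rule. It stands that testing in every phase is a natural reading and not an explicit statement. But 7.A sits under efficacy, and Section 8 says descriptive where that is meant (8.H on mania ratings, 8.I on MRI). 8.J is the only part of Section 8 that names hypothesis tests, and it ties its time points to participation in the phases.

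Stronger readings are tempting, and the documents do not support them:

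- *A reader might infer that the plan would hide a hearing effect that levels off after one course.* It would not. Such an effect could be seen in the randomised Phase I contrast and in the active arm's paired test there.
- *A reader might infer that Phase II results will be presented as active against sham.* Nothing says so. SAP Section 1.C describes Phase II by sequence (sham to active, active to active), and in Phase II grouping by original arm coincides with one versus two active courses.
- *A reader might infer that no unexposed subjects remain in Phase III.* Some who benefited on sham may have had no active TMS.
- *A reader might infer that the Phase I t-test is biased.* A t-test on change is valid under randomisation; it only gives up precision. The baseline test is uninformative but harmless.

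It also stands that little depends on these p-values. The success criteria in SAP Section 2.D concern HAMD24, and the DSMB reports listed in SAP Attachment 2 do not include audiometry.

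**Conclusion.** The concern holds as a minor one. 8.J leaves open, and on its natural reading requires, t-tests at the end of Phases II and III that are not randomised comparisons of active with sham. A null result at the end of Phase II would not by itself show the absence of a hearing effect, and a positive one could reflect cumulative dose or selection.

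The count of 80 tests depends on that reading; if the sponsor intended Phase I only, it is 32. The chance expectations also assume a 5% level that 8.J does not state. The precision gain from ANCOVA depends on an assumed correlation and is a secondary reason for change. The Phase I hearing comparison is sound as planned, and the efficacy conclusions are untouched.

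**What to change.** Amend SAP Section 8.J as follows:

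- Limit between-group hearing tests to the end of Phase I.
- At each frequency, use ANCOVA of the week 6 threshold on arm and baseline threshold, and report the adjusted difference with a confidence interval.
- Drop the baseline significance test and keep the baseline summary statistics.
- Keep the within-arm change in Phase I. The sham coil is acoustically matched, so an effect of noise common to both arms would not show in the between-arm difference.
- Report Phases II and III descriptively, by treatment sequence or by number of active courses received, with a sentence that matches 7.A.

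The cost is SAP wording and table shells. There are fewer tests, and no new data or visits are needed. If Phase I only was always intended, the sentence limiting the tests removes the main ambiguity.

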## Section 9. Other Analyses

## A. Concomitant Medications:

A listing of all permitted concomitant medications used will be provided, including a listing of the proportion of patients who received any concomitant medications listed on the Excluded Medications List.

Subjects were allowed to take non-psychotropic medications and limited medications for sleep and breakthrough anxiety medications. These medications were all to be clearly documented regarding dates of administration, not just dates of prescription. Psychotherapy was allowed if consistent in focus and frequency throughout study. Other non-behavioral or psychological therapies were allowed.

Table 10.	Descrip	otive ir	nclusion	of medi	cations	and o	other	therap	pies	should	be i	included b	y group	in all
phases.	_							-	-					

Variable Name	Туре	Items
Concomitant psychotropic		
medication		
Anxiolytic	Categorical	By medication
Sleep medication	Categorical	By medication
Antidepressant	Categorical	By class (SSRI, SNRI, Other)
Other non-AD	Categorical	By class (Hormone,
		Antimigraine, Anti-convulsant)
Concomitant non-psychotropic		
medication		
NSAID	Categorical	By class
Other	Categorical	By class
Concomitant Therapy		
Psychotherapy	Categorical	Yes/No
Other	Categorical	By therapy

## **B.** Study Blinding:

The Treatment Expectations and Experience Questionnaire (TEEQ) was completed prior to baseline and after acute treatment course during phase I. Parents were only required to complete forms in subjects under 18 but could voluntarily provide input. This data will be analyzed to characterize the impression of patient and parent when completed. The questionnaire responses will be analyzed descriptively with frequencies and percentages. If p-values are provided, they will be for informational purposes only.

## C. Suicidality Change Scores in HAMD:

Change from baseline will be assessed for all timepoints in phase I. This data will be exploratory only and not correlated for any decisions of suicidality.

## Attachments

Attachment I. Scoring Algorithms and Conventions for Major Symptom Assessme	ents:
---	-------

Assessment Tool	Scoring Methods/Conventions
Hamilton Depression Rating	Total Score –
Scale, 24 and 17 Item versions	17 Item Version: Sum of items 1 through 17
(HAMD24, HAMD17)	24 Item Version: Sum of items 1 through 24
	Response –
	Criterion for both versions: $\geq$ 50% reduction compared to baseline
	(Visit 2) total score
	Remission –
	Criterion for HAMD17: Total score < 8
	Criterion for HAMD24: Total score < 11
	Factor Scores –
	Anxiety/Somatization: Total of items 10, 11, 12, 13, 15, 17
	Core Depression: Total of items 1, 2, 3, 7, 8
	Maier: Total of items 1, 2, 7, 8, 9, 10
	Gibbons: Total of items 1, 2, 3, 7, 9, 10, 11, 14
	Retardation: Total of items 1, 7, 8, 14
	Sleep: Total of items 4, 5, 6
Montgomery-Asberg	Total Score –
Depression Rating Scale	Sum of items 1 through 10
(MADRS)	Response Criterion: $\geq$ 50% reduction compared to baseline
	Remission Criterion: Total score < 10
CDRS-R	Total Score –
	Child Rating Scale score: Sum of Items 1 through 17
	Response Criterion: $\geq$ 50% reduction compared to baseline
	Remission Criterion: Total score < 28
Clinician Global Impressions	Integer score on 7 point scale
– Severity (CGI-S)	Item Score and Categorical Distribution reported
	Response Criterion: Score of 3 or less
	Remission Criterion: Score of 2 or less
QIDS-A17-SR	Total Score –
	Sum of the following:
	1) Highest score of any sleep item (Items 1 thru 4)
	2) Highest score of either the mood sad or mood irritable item
	(Items 5 or 6) $(1 + 1)$
	3) Highest score on any 1 appetite/weight item (Items 7 thru 10)
	4) Items 11, 12, 13, 14, 15 each scored as reported
	5) Highest score on either of the 2 psychomotor items (Items 16 or 17)
	Response Criterion: $\geq$ 50% reduction compared to baseline
	$\overline{\text{Remission}}$ Criterion: Total score < 6

## Attachment 2. Data Safety Monitoring Board Reporting:

A Data Safety Monitoring Board is convened for this study. The DSMB will be provided with periodic reports which will include the following information:

#### **Summary of Serious Adverse Events**

The DSMB will receive report sof all serious adverse events that occur during the course of the study. This will include serious adverse events that are considered either related or unrelated to the study device. In the event of the occurrence of a serious adverse event that is considered related to the study device and unexpected based on the labeled safety profile of the device, the DSMB will be asked to recommend an action on the future conduct of the study.

#### Special Safety Topic: Evidence for Deterioration of Illness/Emergent Suicidality:

The Columbia Suicide Severity Rating Scale (C-SSRS) will be used in this study to measure the occurrence of suicidal events and behavior. The DSMB will be provided with the following specific reports from the C-SSRS:

3) Table: Number of Patients with Suicidal Ideation, Suicidal Behavior, and Self-Injurious Behavior with Suicidal Intent (following the format of Table 1 described in the C-SSRS Rating Guide)

Note: This table will report the proportions of patients between active and sham conditions who report positive response on the suicidal ideation items (1-5), the suicidal behavior items (6-10) by item.

4) Table: Shift Table to Demonstrate Changes in C-SSRS Categories from Baseline During Treatment (following the format of Table 3 of the C-SSRS Rating Guide)

Note: This table will report the proportion of patients between active and sham conditions who report positive response on the suicidal ideation items (1-5), the suicidal behavior items (6-10)
